**Bar and Ball Joint Overdentures Surface Roughness and Microbial Adherence**

**NCT (not available)**

**January 5, 2016**

## STUDY PROTOCOL

In the treatment of the mandibular edentulous the implant-retained overdenture has been shown to have advantages in support, retention, stability and esthetics (Stellingsma et al., 2005; Portmann and Galuser, 2006) improving masticatory efficiency, decreasing anterior bone loss and injury in soft tissues, increasing comfort, satisfaction and improvement of the patient's health quality (Visser et al., 2006). According to the type of anchorage recommended we have the implant-retained mandibular bar overdenture (BOD) and implant-retained ball joint overdenture (BJOD). Bar anchors are retention systems that provided adequate support for rehabilitation (Degidi and Piatelli, 2003; Elsyad et al., 2014). By the other side the ball joint are axial anchors with retention system through threaded connections for mandibular prosthetic reconstruction. It is considered that regardless of the retention system the adjustment must be passive to the implants (Van Kampen et al., 2003). The structure of the overdentures consists of thermoplastic polymethacrylates which are derived from ethylene and contain a vinyl group resulting from the polymerization of methacrylic acid or its derivatives (Lang et al., 2003). These polymethacrylates must be resistant to fracture and flexion, properties that can be increased through zirconia or amorphous silica particles (Panyayong et al., 2002; Uzun and Keyf, 2003). Possibly the immersion of some oral restorations in agents cleaners alter their structural stability (Senna et al., 2011). It is considered that the absence of porosity and dimensional stability increase the surface quality of the restorations, influencing the preservation of the mucous tissues through surfaces that facilitate the patient's oral hygiene. Therefore, an important factor in reference to the quality of the mouth restorations is the surface roughness with importance in the preservation of the oral health in relation to the surrounding tissue (Yap et al., 2004; Guler et al., 2005; Bollen et al., 1997). There are differences in roughness values in various thermoplastic polymethacrylates (Berger et al., 2006). The surface quality of the restorations and their relationship with the gingival tissues enable smoother surfaces to maintain the health of oral tissues avoiding the inflammation of them. The surfaces of the overdentures are available as substrates for the development and growth of microorganisms. The oral cavity presents more than

seven hundred bacterial species (Busscher and Van der Mei, 1997) and overdentures implant-retained are susceptible to the accumulation of microorganisms with adhesion capacity such mold and yeast and mesophyll aerobe. The yeasts are unicellular fungi which reproduce by budding and transverse division and the mold is formed by hyphae the whole of which forms a mycelium. The mold and yeast which cause pathology in humans are dimorphic 2 to 4 um in diameter (Radford et al., 1999). Other microorganisms with adhesion capacity are mesophyll aerobes which include bacteria that develop in the presence of free oxygen of 0.5 to 2 um in diameter (Daniluk et al., 2006; Busscher et al., 1986). The permanence of BOD and BJOD depends on several factors, one of them being the surface roughness (Ra) and its relation with the adhesion of microorganisms. The objective of the study was to compare the surface roughness (Ra) of BOD compared to BJOD in relation to the adhesion of mold and yeast and mesophyll aerobe at 30 and 180 days of permanence in the oral cavity in order to establish if there are differences in surface roughness and which of these overdentures are characterized by their lower roughness and adherence of mold and yeast and mesophyll aerobe which is an important aspect to be considered in the rehabilitation of mandibular total edentulous patients with implants due to their influence on oral health.

## **MATERIALS AND METHODS**

The study presents the results of a sample of ten patients randomly assigned to receive implant-retained overdentures and divided into two parallel groups of five participants in a single-blind trial at a follow-up period of 30 and 180 days permanence in the mouth. Five overdentures were made for each group: Group 1: BOD: five systems titanium bar CARES® and synOcta® Straumann® Dental Implant System, Holding AG Inc., Basel, Switzerland (BOD). Group 2: BJOD: five systems ball joint Klockner® Implant System; Soadco Inc., Escaldes-Engordany, Andorra were used in two parallel groups of five participants, in an essay to simple blind person. The protocol was approved by Institutional Review Boards affiliated with the researcher. All participants gave informed consent. The inclusion criteria of

the patients for the study were: Total edentulous mandible from 50 to 60 years of age and absence of systemic conditions. The exclusion criteria of the patients for the study were: hyperplasia and history of periodontal disease, patients with local and/or systemic antimicrobial treatment within 72 hours prior to evaluation during the study and signs of severe oral parafunction (Figure). Selected patients underwent surgery with Tapered Effect Implants Straumann® and Klockner Implant System®. For the manufacture of the overdentures in both groups it was used as material of choice Lucitone 199® (Dentsply International Inc. York, PA) and for the adaptation of the retention systems it was used Softreliner Tough Soft® Tocuyama Dental Corporation Inc., Japan. The working protocol for determining the BOD Ra and BJOD Ra and the adhesion of molds and yeasts and mesophyll aerobics was carried out entirely by an investigator and the following working methodology was considered: Information to the patient of the research work to be performed. Obtainment of clinical data and patient informed consent. Patients were randomly assigned to group 1 and group 2. The saliva sample was obtained in each patient for the microbiological before the installation of the overdentures. BODs and BJODs were installed in each patient and according to each case. The BOD and BJOD were removed at 30 days for surface roughness evaluation (Ra:µm) and the evaluation of the adhesion of mold and yeast and mesophyll aerobe (CFU/ml). For the study at 180 days the BODs and the BJODs were installed in each patient. BODs and BJODs were removed after this time to proceed to the evaluation of surface roughness and adhesion of mold and yeast and mesophyll aerobe under the same parameters mentioned above.

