#### **Adherence mold and yeast and mesophyll aerobe to BOD and BJOD, Surface roughness (Ra), and Statistical Analyses**

Microbial populations have been controlled in the saliva at initial time and adherence at 30 and 180 days after the overdentures in the mouth. The saliva sample was obtained from the

patient in a sterile sputum collection bottle through a sterile solution. The overdenture samples were extracted and processed for analysis. Each sample was submerged in  $\frac{1}{4}$  sterile Ringer and subjected to vigorous ultrasound shaking. From each of the microbial suspensions, successive dilutions were made to determine the total number of viable microorganisms present. Total count of mold and yeast and total count of mesophyll aerobe were performed.

The surface roughness of BOD and BJOD was determined with the rugosimeter the Mitutoyo Surfest SJ-301® (Mitutoyo Corporation Inc., Kanagawa, Japan), through a displacement force of 4mN and of the tray to 0.5 mm/s and back to 1 mm/s (Murtra and Arcís, 1999). The roughness profile Ra was evaluated and determined in microns ( $\mu\text{m}$ ) through five readings for each of the samples in the study respectively.

The results of BOD and BJOD were compared for the determination of Ra and the adherence of mold and yeast and mesophyll aerobe. For this, we used the statistics Shapiro-Wilk, T and the Pearson Correlation Coefficient to determinate the relationship between the study variables. For data processing and analysis the Software Package for Social Sciences (SPSS) version 24.0 was used.

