## **Bar and Ball Joint Overdentures Surface Roughness and Microbial Adherence**

**NCT (not available)**

**January 5, 2016**

## **STATISTICAL ANALYSIS PLAN**

The results of bar overdentures BOD and ball joint overdenture BJOD will be compare for the determination of Ra and the adherence of mold and yeast and mesophyll aerobe. For this, will be used the statistics Shapiro-Wilk, T and the Pearson Correlation Coefficient to determinate the relationship between the study variables. For data processing and analysis the Software Package for Social Sciences (SPSS) version 24.0 will be used.

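### Should the pre-installation saliva counts be used in the comparison of microbial adherence between bar and ball-joint overdentures?

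*Protocol*

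**What the plan says.** Ten patients are randomised, five to the bar overdenture (BOD) and five to the ball-joint overdenture (BJOD). In the working sequence under MATERIALS AND METHODS, the Protocol has "Patients were randomly assigned to group 1 and group 2" and then "The saliva sample was obtained in each patient for the microbiological before the installation of the overdentures". Adherence is counted on the removed overdenture at 30 and 180 days.

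The Protocol section on adherence, roughness and statistical analyses says: "Microbial populations have been controlled in the saliva at initial time and adherence at 30 and 180 days after the overdentures in the mouth". It describes saliva collection "in a sterile sputum collection bottle through a sterile solution". After describing how the overdenture samples were suspended and diluted, it adds: "Total count of mold and yeast and total count of mesophyll aerobe were performed".

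The SAP compares the arms on roughness (Ra) and adherence only: "For this, will be used the statistics Shapiro-Wilk, T and the Pearson Correlation Coefficient to determinate the relationship between the study variables". The Protocol's analysis paragraph names the same three methods. Neither text names saliva as a covariate, a reference for change, or a variable to be summarised by arm.

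**The concern.** Each patient gives a microbiological sample before the overdenture is fitted, and the analysis text then makes no named use of it. In a trial of ten patients, one arm can easily start with a heavier oral load by chance. If saliva load predicts adherence, a chance gap carries over into the unadjusted difference between BOD and BJOD, and a reader with no saliva figures could not tell. Adjusting for a prognostic baseline is also commonly recommended because it can gain precision, and here the sample has already been collected.

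At stake would be the reading of the two adherence comparisons (mold and yeast, mesophyll aerobe) at each visit. Surface roughness is not affected.

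**Working it through.** **Inputs.** From the documents: n = 5 per arm, randomised, parallel groups; planned methods Shapiro-Wilk, T and Pearson. Assumed, because the documents do not say: two-sided 5% level, normally distributed log counts, and a within-arm saliva–adherence correlation rho from 0 to 0.7. The documents give no sample-size or power figure to reproduce.

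**1. How often the arms start apart.** The standard error of the difference in mean saliva log count is sqrt(2/5) = 0.632 SD.
- P(gap > 0.5 SD) = 2 × [1 − Φ(0.5/0.632)] = 0.43.
- P(gap > 1 SD) = 2 × [1 − Φ(1/0.632)] = 0.114.
- For at least one of two organism groups: 0.114 if fully correlated, 1 − (1 − 0.114)² = 0.215 if independent.

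**2. What a gap does to the t-test.** A saliva gap D shifts the expected unadjusted adherence difference by rho × D. At a gap of exactly 1 SD the shift is 0.3, 0.5 or 0.7 SD for rho 0.3, 0.5 or 0.7, and the simulated false-positive rate is about 6%, 8% or 11%. Averaged over all gaps beyond 1 SD the rates are higher, as in the first row below. The table compares the t-test (8 df) with ANCOVA on one saliva covariate (7 df).

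| Quantity | rho 0.3 | rho 0.5 | rho 0.7 |
|---|---|---|---|
| False positives, gap > 1 SD: t-test | 7.6% | 12.1% | 19.1% |
| False positives, gap > 1 SD: ANCOVA | 5.1% | 5.0% | 5.0% |
| False positives, other allocations: t-test | 4.7% | 4.1% | 3.2% |
| Mean 95% CI half-width, gap > 1 SD: t-test | 1.41 SD | 1.41 SD | 1.41 SD |
| Mean 95% CI half-width, gap > 1 SD: ANCOVA | 1.77 SD | 1.61 SD | 1.33 SD |
| Trials with wider ANCOVA interval, gap > 1 SD | 87% | 71% | 43% |
| Power at 1.5 SD, gap > 1 SD: t-test | 54% | 53% | 52% |
| Power at 1.5 SD, gap > 1 SD: ANCOVA | 40% | 46% | 61% |

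The t-test averages to its nominal level. At rho 0.5, 0.114 × 12.1% + 0.886 × 4.1% = 5.0%, and the other columns give the same.

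**3. Whether adjustment pays overall.** The average ANCOVA variance factor is (1 − rho²) × [1 + 1/(2n − 4)] = (1 − rho²) × 7/6. The critical value rises from 2.306 (8 df) to 2.365 (7 df). The CI width relative to the t-test is (2.365/2.306) × sqrt[(1 − rho²) × 7/6], which is 1.11 at rho 0, 1.06 at 0.3, 0.96 at 0.5 and 0.79 at 0.7. It equals 1 at rho = sqrt[1 − (2.306/2.365)² × 6/7] = 0.43. Simulated power at 1.5 SD is 55% for the t-test, and 49%, 52%, 55%, 60% and 76% for ANCOVA at rho 0, 0.3, 0.4, 0.5 and 0.7. Break-even is therefore about 0.4 overall. Among allocations with a gap above 1 SD, the intervals match only at about 0.65.

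**4. Whether rho could be learned from the trial.** With ten patients in two arms, an observed within-arm correlation of 0.4 has Fisher z = 0.424 and SE = 1/sqrt(10 − 1 − 3) = 0.408. The 95% CI is −0.36 to 0.84, which covers both harm and gain.

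**5. Whether the sample is a true baseline.** The Protocol lists it after random assignment and dates it only as before installation. It also says "Selected patients underwent surgery with Tapered Effect Implants Straumann® and Klockner Implant System", while group 2 is described as "Group 2: BJOD: five systems ball joint Klockner® Implant System", so the implant systems differ by arm. Whether saliva was taken before or after surgery is not stated. Suppose the arm had already shifted saliva by an assumed 1 SD and adherence did not differ. ANCOVA would then report a false difference of rho × 1 SD = 0.30, 0.50 or 0.70 SD, with false-positive rates of 6.6%, 10.4% and 20.7%. The t-test stays at 5.0%.

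**The case for a change.** The strongest case for acting is that the omission is real and the remedy is cheap. The verb in "Microbial populations have been controlled in the saliva at initial time and adherence at 30 and 180 days after the overdentures in the mouth" cannot be read as statistical adjustment, because it also governs the adherence counts and so means measured. Pearson for undefined study variables might take in saliva, but a correlation is neither a by-arm description nor an adjusted contrast. When the gap is large, the conditional false-positive rate of the t-test does rise, and adjustment restores it to about 5%. A by-arm table needs no new samples and would show the reader whether the arms started level.

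The textual points stand, and so does the arithmetic. What does not follow is a change to the plan. The table and a sentence on sampling time would add description but leave every planned estimate and test as it is. The SAP is a single paragraph that lists no descriptive tables at all, so a missing saliva table reflects its brevity, and an analyst would ordinarily supply one. The adjusted model needs several facts the documents do not give: a sample that the arm could not have influenced, uniform saliva volume and dilution, counts of the same two organism groups in saliva (plausible from the text but not explicit), and a sufficiently high rho. Even then, parallel slopes could not be checked with five per arm.

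**Conclusion.** The concern does not call for a change. The planned unadjusted comparison is a legitimate analysis of randomised arms and holds its nominal error rate over all allocations. Adjustment for saliva is a trade-off: it protects against a large chance gap, expected in about 11% of allocations per organism group, but it costs up to about 6 points of power (55% to 49%) if rho is near 0. It also gives a wider interval in most of the imbalanced trials it is meant to help, unless rho is high. Saliva is not a baseline measure of adherence on the overdenture, and its timing leaves open a bias that the t-test avoids.

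This rests on normal log counts, a two-sided 5% level and rho between 0 and 0.7, none of which the documents state. Firm evidence of a correlation well above 0.4, with confirmation that the arm could not have affected the sample, would make an adjusted sensitivity analysis attractive. Neither is in the documents. Listing saliva counts by arm, with the time of sampling, is a matter for the trial report.

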#### **Adherence mold and yeast and mesophyll aerobe to BOD and BJOD, Surface roughness (Ra), and Statistical Analyses**

Microbial populations have been controlled in the saliva at initial time and adherence at 30 and 180 days after the overdentures in the mouth. The saliva sample was obtained from the

patient in a sterile sputum collection bottle through a sterile solution. The overdenture samples were extracted and processed for analysis. Each sample was submerged in  $\frac{1}{4}$  sterile Ringer and subjected to vigorous ultrasound shaking. From each of the microbial suspensions, successive dilutions were made to determine the total number of viable microorganisms present. Total count of mold and yeast and total count of mesophyll aerobe were performed.

The surface roughness of BOD and BJOD was determined with the rugosimeter the Mitutoyo Surfest SJ-301® (Mitutoyo Corporation Inc., Kanagawa, Japan), through a displacement force of 4mN and of the tray to 0.5 mm/s and back to 1 mm/s (Murtra and Arcís, 1999). The roughness profile Ra was evaluated and determined in microns ( $\mu\text{m}$ ) through five readings for each of the samples in the study respectively.

The results of BOD and BJOD were compared for the determination of Ra and the adherence of mold and yeast and mesophyll aerobe. For this, we used the statistics Shapiro-Wilk, T and the Pearson Correlation Coefficient to determinate the relationship between the study variables. For data processing and analysis the Software Package for Social Sciences (SPSS) version 24.0 was used.

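### The plain Pearson coefficient can mix a between-arm difference with a within-arm link between Ra and adherence; an arm-adjusted coefficient at each visit should stand beside it.

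*Protocol*

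**What the plan says.** The last paragraph of the Protocol's introductory section sets out to compare the Ra of bar and ball joint overdentures "in relation to the adhesion of mold and yeast and mesophyll aerobe at 30 and 180 days of permanence in the oral cavity". It also wants to establish "which of these overdentures are characterized by their lower roughness and adherence of mold and yeast and mesophyll aerobe". So both the relation and the arm difference belong to the objective.

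Under Materials and Methods the sample is "ten patients randomly assigned to receive implant-retained overdentures and divided into two parallel groups of five participants". Ra and adherence are evaluated at 30 days. Then, "For the study at 180 days the BODs and the BJODs were installed in each patient", and both are evaluated again.

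The statistical paragraph of the Protocol says "The results of BOD and BJOD were compared for the determination of Ra and the adherence of mold and yeast and mesophyll aerobe" and names three tools: Shapiro-Wilk, T and "the Pearson Correlation Coefficient to determinate the relationship between the study variables". The SAP repeats this in the future tense, again with the "Pearson Correlation Coefficient to determinate the relationship between the study variables", and adds no detail. Pearson is the only measure of association. No partial correlation, regression or mixed model appears in either document. Neither says whether the coefficient is computed by arm, across arms, by visit or across visits.

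**The concern.** A plain Pearson coefficient across ten patients in two arms has two sources: the link among patients within an arm, and the gap between the arm means. When both variables differ by arm, the gap alone produces a correlation. It can also cancel a real link if the two differences run in opposite directions. An arm difference in roughness and in adherence is what the trial sets out to look for, so this condition cannot be ruled out in advance.

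A reported coefficient could therefore mean that rougher dentures carry more organisms within a given retention system, or only that one system is both rougher and more colonised. The plan gives the reader no way to tell these apart.

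**Working it through.** **No figure to reproduce.** The documents give no alpha, SD, effect size, within-patient correlation or power calculation.

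**Inputs from the documents:** 5 + 5 patients, two visits, and two counts (mold and yeast; mesophyll aerobe).

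**Assumptions:** two-sided 0.05, normal data, SD of 1 within arm, no dropout. Error rates and power come from 200,000 simulated trials per setting.

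**Critical values,** |r| = t/√(t² + df):
- plain, n = 10, 8 df: 0.632
- adjusted for arm, n = 10, 7 df: 0.666
- one arm, n = 5, 3 df: 0.878
- 20 stacked points, 18 df: 0.444

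**Reading 1: arms combined at one visit.** With no within-arm link and a shift of d SD in both variables, the induced correlation is (d²/4)/(1 + d²/4). At d = 1 this is 0.25/1.25 = 0.20. At d = 1.5 it is 0.5625/1.5625 = 0.36.

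| Shift in both (SD) | False positives, plain | False positives, arm-adjusted |
|---|---|---|
| 0 | 5.0% | 5% |
| 0.5 | 5.3% | 5% |
| 1 | 8.7% | 5% |
| 1.5 | 19% | 5% |

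A shift in one variable only leaves the plain test at 5%. With opposite shifts of 1.5 SD and a true within-arm r of 0.7, the mean plain r is about 0.01, so the link is hidden. The adjusted coefficient detects it 62% of the time.

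**Reading 2: both visits stacked as 20 independent points.** With no link and no shift, false positives are 5%, 6%, 8% and 14% at a within-patient correlation of 0, 0.3, 0.5 and 0.8 in both variables.

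**Reading 3: each arm at each visit.** The test is valid, but n = 5. A true r of 0.5 is detected 13% of the time and a true r of 0.9 is detected 67% of the time.

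**Intervals around an observed r of 0.5** (Fisher z, where z = 0.549):
- one arm, SE 1/√2: −0.68 to 0.96
- plain, n = 10, SE 1/√7: −0.19 to 0.86
- arm-adjusted, SE 1/√6: −0.25 to 0.87

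**Cost of adjusting.** At a true r of 0.5 with no arm shift, power falls from 33% to 29%. If the arm acts on the count only through Ra, power falls from 40% to 29% at a 1 SD shift in Ra, and from 57% to 29% at 2 SD.

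**The case against.** The strongest reply is that adjustment is not always an improvement. With no arm shift, or a shift in one variable only, the plain test already holds 5% and adjusting only loses power. If the retention system affects adherence through roughness, the arm contrast is part of the relation and adjustment removes it. This stands. A reader might infer that the adjusted coefficient is better under every reading, or should be the main estimate. The documents do not support that, because the two coefficients answer different questions.

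The shifts are also assumed. Both arms use the same denture base material and soft liner, and nothing in the documents supports 1 to 1.5 SD in both variables. This too stands, although it does not rule out an arm difference.

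A reader might infer that the plan stacks visits or pools arms. No section says so. The objective names the two time points, and Materials and Methods describes two separate evaluations. The wording also permits a by-arm, by-visit analysis. Stacking is a reading to close off, not an error that the plan commits.

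Nor does the remedy reduce multiplicity. Two coefficients for each of two counts at two visits make eight, the same number as separate per-arm coefficients. With no link and visits taken as independent, the chance that at least one of the eight is nominally significant is a little under one in four with no arm shift, and 38% with a 1 SD shift in both variables.

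Finally, all the figures assume normal data, while adherence is a CFU/ml count whose scale for the correlation is not stated. If the log count has r = 0.5 with Ra and a log-SD of 1 to 2 (assumed), adjusted power on raw counts is 23% to 17%, against 29% on logs. That is a further gap and does not remove this one.

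**Conclusion.** The point holds in a limited form. The only association method in the plan cannot separate a within-arm link from a between-arm difference if the arms are combined. That matters when both Ra and the count differ by arm: 9% false positives at 1 SD and 19% at 1.5 SD, negligible at 0.5 SD or below, and none when only one variable differs. Opposite shifts can hide a real link. Stacking visits would be anti-conservative if both variables correlate within patient, and per-arm coefficients are valid but very imprecise.

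All sizes rest on assumed shifts, normality and a two-sided 0.05 level. With ten patients no version supports a firm conclusion. The gain is in what the coefficient can be said to mean. The SAP should be amended, and the change is modest.

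**What to change.** Replace the Pearson sentence in the SAP, and match it in the Protocol, with the following:
- At each visit separately, with the patient as the unit, report two coefficients of Ra with each count.
- The first is the plain Pearson coefficient (n = 10), labelled as including the between-arm difference.
- The second is the partial correlation adjusted for arm (7 df), labelled as the within-arm association.
- Give each a 95% CI, and label all of them exploratory. Neither needs to be named the main one.
- Add a scatter plot marked by arm for each pairing.
- Do not treat the two visits as independent points.

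This needs no new data. The adjusted coefficient has the power loss shown above and a slightly wider interval. It assumes a similar relation in both arms, which five patients per arm cannot test well; the plot is a rough check only. Because eight coefficients are printed, the SAP should state that no significance claim rests on any single one.
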